## 1. STUDY SUMMARY

Study Title	Role of Transcranial Direct Current Stimulation to Decrease Impulsivity and Compulsivity in Individuals with Obesity
Study Design	Double-blind, randomized, sham-controlled pilot clinical study
Primary Objective	
Primary Objective: To determine if there is a treatment-related decrease in measures of impulsivity and compulsivity with tDCS compared to sham
 
Hypothesis: tDCS treatment decreases impulsivity and compulsivity.

Secondary Objective(s)	
Secondary Objectives: (1) To compare tDCS treatment-related change in weight loss compared to sham (randomized intervention) in individuals prior to undergoing their 16 week structured behavior modification weight loss program (usual care) in the Minneapolis VAMC's Move Mass Program
 
Hypothesis: tDCS treatment leads to weight loss
 
(2) To examine the history of brain injury (no TBI, single TBI, multiple TBI) in individuals with obesity as a possible factor in impulsive and compulsive eating.
 
Hypothesis: TBI as a co-morbid condition may have some impact on eating behaviors.

Research Intervention(s)/Investigational Agents	tDCS (Starstim Noninvasive Wireless neurostimulator)
IND/IDE # (if applicable)	Class IIa device
Study Population	500 Veterans will be screened to enroll up to 50 Veterans. Subjects will be recruited from Minneapolis VAMC's Move Mass Behavior Modification Classes
Sample Size (number of participants)	20 (10 will undergo tDCS and 10 will undergo sham procedure). All will undergo Brain HQ task training to enhance executive function.
Study Duration for Individual Participants	About 3-4 months

## 2. Abstract

**Objectives.** Impulsivity and compulsivity are two psychological factors which contribute to addictive behaviors. Impulsivity is characterized by lack of foresight and planning, and excessive risk taking. Impulsivity is a characteristic of poor executive functioning, reflective of deficits in goal-oriented behavior and self-regulation. Impulsivity is common to a number of psychiatric conditions which contribute to high morbidity and mortality in Veterans such as substance abuse disorders, post-traumatic stress disorder, and traumatic brain injury (TBI). Impulsivity has been implicated in refractory obesity, in both bariatric and non-bariatric subjects (Sutin 2011, Filbey 2017, Gunstad 2017, Galioto 2016). Individuals with food impulsivity report out of control eating; they may report binging and/or cravings. Compulsivity, characterized by inability to break old habitual behaviors, may also play a role in refractory obesity. Transcranial direct current stimulation (tDCS) has been shown in other settings to reduce impulsivity. Coupled with brain training tasks to strengthen key circuitry involved in impulse control, the prefrontal cortex, tDCS has the potential to reduce impulsivity and compulsivity in individuals with obesity, with the potential for therapeutic application as a non-pharmacologic treatment for obesity in individuals with food impulsivity.

**Research plan and methods.** We plan to enroll up to 50 individuals and complete studies in 20 individuals involved with the Minneapolis VAMC's Move Mass weight management clinic. Participants, who report that they tend to have out-of-control eating at least once per week, will be randomized to either active or sham tDCS, two 13-minute sessions separated by 20 minutes, for five consecutive treatment days; both groups will undergo brain training tasks during the treatments. After they complete the sessions subjects will complete a 16-week long structured Move Mass Behavior Modification program (usual care). In addition to the brain training tasks during the stimulation periods, subjects will complete a food-impulsivity related questionnaire (the Binge Eating Scale [BES]) and other instruments at several timepoints during the study. The effect of the active vs. sham treatment to reduce measures of impulsivity and improve measures of executive function will be assessed over time. As a secondary aim we will evaluate treatment effect on weight loss and examine the possible relationship to TBI.

**Clinical relevance.** Refractory obesity, like other conditions with an addictive component, is in part related to impulsivity and inability to change compulsive behavior. More effective treatments are needed for this condition which significantly impacts morbidity and mortality in Veterans and non-Veterans. Safer, more effective treatments, including non-pharmacologic treatments which make use of the brain's own neuroplasticity to enhance function and heal or strengthen regions involved in impulse control represents an exciting new therapy for impulse control in individuals with obesity.

### 3. Objectives and Specific Aims

- a. Purpose: The primary purpose of this study is to determine if tDCS coupled with executive function training decreases impulsivity and compulsivity in individuals with obesity. As a secondary aim, we will evaluate whether tDCS when coupled with executive functions training enhances weight loss in individuals with obesity attempting to lose weight in a structured behavior-modification based program.
- b. Our **specific aims** are as follows:
  - i. **Aim 1:** To determine if tDCS with executive function tasks vs. sham paired with executive function tasks reduces impulsivity and compulsivity in individuals who report out of control eating and are enrolled in a 16 week structured behavior modification-based weight loss program
  - ii. **Hypothesis 1:** tDCS treatment decreases impulsivity and compulsivity in individuals with obesity who are enrolled in a structured behavioral modification weight loss program.
  - iii. **Aim 2 (secondary):** To test whether tDCS treatment, paired with executive function tasks, enhances weight loss compared to sham paired with executive function tasks in individuals who report out of control eating and are enrolled in a 16-week structured behavior modification-based weight loss program
  - iv. **Hypothesis 2:** tDCS treatment with executive functions training enhances weight loss in individuals with obesity who are enrolled in a structured behavioral modification weight loss program.
  - v. Aim 3: To examine the history of brain injury (no TBI, single TBI, multiple TBI) in individuals with obesity as a possible factor in impulsive and compulsive eating.
  - vi. Hypothesis3: TBI as a co-morbid condition may have some impact on eating behaviors.

In addition to the hypotheses and aims above, we intend to confirm the findings of Galioto *et al*, and demonstrate that baseline executive function predicts weight loss success (Galioto 2016).

### 4. Background, Significance, and Preliminary Data

Impulsivity and compulsivity are two psychological factors which contribute to addictive behaviors. Impulsivity is characterized by lack of foresight and planning, and excessive risk taking. Impulsivity is a characteristic of poor executive functioning, reflective of deficits in goal-oriented behavior and self-regulation. Impulsivity is common to a number of psychiatric conditions which contribute to high morbidity and mortality in Veterans such as substance abuse disorders, post-traumatic stress disorder and TBI. Impulsivity has been implicated in refractory obesity, in both bariatric and non-bariatric subjects (Sutin 2011, Filbey 2017, Gunstad 2017, Galioto 2016). Individuals with food impulsivity report out of control eating; they may report

binging and/or cravings. Compulsivity, characterized by inability to break old habitual behaviors, may also play a role in refractory obesity.

In our own experience with a non-veteran population followed in the Adult Medical Weight Management Clinic at the University of Minnesota where the average BMI is around 40, 89% of patients self-reported some level of out of control eating and/or craving at intake assessment (manuscript in preparation by PI). With regards to the veteran population at the Minneapolis VA, a large percentage of patients also report cravings for particular foods, binging, or out of control eating. It is also of note that insight into the underlying neurobiology of food impulsivity and/or cravings can also inform understanding of other compulsive, addictive behaviors such as gambling, and drug addictions including alcohol and cocaine abuse. These disorders manifest out of common neurobiological soil, a lack of impulse control.

*Neurobiology underlying food impulsivity/cravings, and impulsivity.* Eating and appetite behaviors are the output of brain networks comprised of homeostatic, reward and executive function components. Homeostatic appetitive centers in the brain include the hypothalamus, including the paraventricular (PVN), Arcuate, lateral, and dorsomedial nuclei. Traditionally, the hypothalamus has been considered an important region for acute and chronic fuel storage sensing, the basis for its homeostatic component to weight regulation. Other important components, brain reward centers, include the central nucleus of the amygdala, the nucleus accumbens, and the nucleus tractus solitaires which respond to other cues such as palatability; these limbic areas may also be affected by other non-homeostatic inputs such as emotions. Brain reward centers are strongly involved in mediating impulsivity- and compulsivity-related behaviors such as addictions, especially when these areas are not able to be adequately regulated by areas involved in executive function such as the prefrontal cortex.

*Inadequate “Gate-keeping”: Executive function and Obesity.* Areas of the brain involved in directing goal-oriented behavior, such as the prefrontal cortex, provide an important counter-balance to the activity of the brain reward centers, not only with regards to the impulse control involved in drug addictions but also with weight regulation. Executive function predicts weight loss success in structured medical weight loss programs (Galioto 2016). Ultimately it is the integrative interaction between and among the homeostatic, reward, and “gate-keeping” regions that determines appetite perception and response to it. There is no effective treatment for impulsivity. The ideal treatment would provide enhancement of function in areas of the brain which govern impulse control and may provide an important, under-appreciated target for obesity treatment.

One common factor to both obesity and executive dysfunction is traumatic brain injury (TBI). Survivors recovering from TBI are at risk for obesity and overweight problems and health conditions, particularly during long-term recovery ([Dreer et al., 2017](#)). Dreer et al. (2017) showed increased prevalence rates of obesity immediately following and with increasing time since injury. Both TBI and obesity have negative consequences on frontal cortical structure and function. Obesity has been associated with atrophy in frontal lobes, with concomitant impaired performance on cognitive testing (Fotuhi & Lubinski, 2013). Cognitive dysfunction, in the domains of attention, impulsivity, and executive function, is a leading cause of disability following TBI (Rabinowitz & Levin, 2014; Wood & McHugh, 2013). Thus, the relationship between obesity and TBI, and their effects on impulsive behavior, are important to consider with regard to identifying factors related to unhealthy weight management and the design of treatment programs.

*Cognitive training coupled with transcranial direct current stimulation for impulsivity.*

1. Cognitive training for reducing impulsivity in healthy subjects. The go/no-go task has been utilized successfully to reduce chocolate eating in female undergraduates with chocolate craving (Houben/Jansen 2011) and beer consumption in heavy alcohol drinkers

(Houben/Nederkoom/Wiers/Jansen 2011) in very short-term studies. While there is evidence that cognitive training may provide potential treatment for impulsivity, with application to obesity management, there is concern that the results from very task-specific cognitive training may not generalize to other desirable behavior change. Unfortunately, cognitive training can be time consuming and in addition to lack of generalization, results of cognitive training may not persist.

**2. tDCS: A tool for reduction of impulsivity and compulsion.** tDCS, even in a single session, has been found to reduce cravings and enhance cue response to negative stimuli in individuals with alcohol use disorder (Boggio 2008). Furthermore, a multiple treatment schedule of tDCS (twice daily for 5 days) was found to help reduce relapse over a 6-month period in subjects with alcohol use disorder (Klauss 2014). Some investigators have found decreased cravings, as measured by questionnaires, after 5 days of treatment and 30 days later (Ljubisavljevic 2016). In preliminary data from members of our team tDCS over the dorsolateral prefrontal cortex was shown to reduce risk-taking impulsivity (see Preliminary Data section below).

**3. Cognitive training with tDCS: complementary therapy to strengthen circuitry deficits which underlie impulsivity and compulsion, a tool for augmentation of neuroplasticity.** Application of tDCS with relevant task-based cognitive training may enhance the function of pathways being stimulated by the task training (Bikson/Rahman 2013). Coupling of tDCS with a broader array of task training, rather than narrow domain-specific component of executive function, may allow for generalization of enhanced executive function and better long term therapeutic results for impulsivity-related disorders, including substance abuse and obesity.

**Significance.** If tDCS can be utilized to enhance plasticity in regions of the brain involved in impulsivity and compulsion, then tDCS combined with cognitive training becomes a powerful non-pharmacologic tool for altering brain circuitry to improve impulsivity and compulsion. This approach has the potential to be applied to a wide range of neurobiological disorders.

**Preliminary data.** Prior work by members of our group demonstrates that the application of tDCS does appear to improve impulse control when applied with tasks which engage regions of the brain involved in executive function. [name] and colleagues conducted a VA-based study in 30 individuals who underwent two 25-minute sessions (active tDCS vs. sham procedure coupled with performance of the Balloon Analogue Risk Task [BART]) for five days followed by sessions at one and two months. Subjects completed questionnaires and behavioral tasks measuring impulsivity (the Risk Task) before and after the intervention. After receiving active tDCS, subjects showed a significant 46% decrease in risky choice in the Risk Task from pre- to post-intervention, which persisted through the one and two-month follow-up sessions. The sham tDCS group showed no significant change in risky choice from pre- to post-intervention.

#### **4. Study Endpoints**

**Primary Endpoint:** decrease in impulsivity and compulsion (as measured by change in NIH Examiner Score) with active tDCS compared to sham

**Secondary Endpoint:** change in weight over the study period

## 5. Study Intervention(s)/Investigational Agent(s)

- a. Description: tDCS and discussion of device handling. We will use the Neuroelectrics Starstim system, a wireless multichannel transcranial current stimulator. Periods of tDCS stimulation of 13 minutes will be twice a day, separated by 20 minutes (Monte-Silva et al., 2013), for five consecutive days (10 total tDCS stimulation sessions). Active tDCS: A 2-mA current will be administered via two circular carbon rubber core electrodes in saline-soaked surface sponges (25 cm^2), placed in a neoprene headcap with marked locations based on the 10-10 EEG system. The anodal stimulating electrode will be at location F4, over right dorsolateral prefrontal cortex (DLPFC) and cathodal electrode at location F3, over left DLPFC. Sham tDCS: For sham stimulation, the electrodes will be placed at the same positions as for active stimulation (F3 and F4), but current will be ramped down immediately after the initial 30 s ramp up period. Thus, participants will feel the initial itching sensation associated with tDCS but will receive no active current for the rest of the stimulation period. This method of sham stimulation has been shown to be reliable (Gandiga, Hummel, & Cohen, 2006). The Starstim software supports the measurement of electrode impedance. Before each training session, the impedance of the electrodes will be checked and verified to be  $\leq 10$  KOhm. During a training session, the impedance is measured every second and if found to be  $> 20$  KOhm stimulation will be terminated for safety. The current and impedance will be recorded for every session.
- b. IND/IDE: The FDA has classified this as a NSR device (an FDA letter for use of this same device in another study by members of our research team for a similar purpose and protocol is included with our IRB packet for this current application)

[figure not shown]
## 6. Study Methods, Procedures, and Statistical Plan

### Study Design:

For this single-site pilot study our statistical approach will be similar to prior work done by members of our team previously, a double-blind, randomized controlled design with participants randomized to either active or sham tDCS. For this study Veterans will be referred as potential candidates because they have obesity and self-report that they tend to have at least one occasion of out-of-control eating per week on average. Participants will be trained on the Brain HQ, an interactive computer software package in which subjects work through a series of structured exercises designed to stimulate neuroplasticity. Participants will be randomly assigned to receive either active tDCS or sham stimulation with their training during one hour session each day( 13 minutes of stimulation , 20 minute stimulation break, followed by 13 more minutes of stimulation) over five days. A 2 mA current will be applied with two 25 cm^2 saline soaked electrode sponges with anode at F4 (right) and cathode at F3 (left) concurrent with the Brain HQ. To evaluate generalization, an untrained NIH Examiner Battery sub-set testing 4 modalities of executive function will be performed before and after the five days of training. Subjects will then go through the Move Mass Behavior Modification after completing the five days of treatment. (This 16-week structured behavior modification program of bi-weekly sessions is usual care for these participants.) Participants will return for the trained and untrained testing at V7 (halfway through the behavior modification course) and V8 (final study visit to occur after the behavior modification course) follow-up sessions without stimulation. For the trained Brain HQ tasks, growth curve analysis (GCA) examining individual variation of the

growth rates over time will be done (across the 5 days of tDCS sessions and the subsequent follow-ups) to examine for change in individual and group trajectories over time. For the untrained NIH Examiner tasks, GCA will be used to evaluate for individual and group effects in executive function in the four domains of the NIH Examiner Battery from pre- to post-treatment and through follow-up sessions. We will also compare pre- and post- treatment results in the cravings and binging questionnaires within and between groups.

Figure 1: Study Visit Schedule

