### **Study Procedures:**

Five hundred individuals will be screened with the goal of consenting 50 patients and 20 patients completing the study. The study consists of 8 study visits including 4 testing days, one before (V2) and one on the day of the fifth session of tDCS (V6) followed by the structured 16-week long behavior modification class, and test visit half way through the 16-week class (V7) (2 months into the behavior modification class), and a final test visit 2 months later (+/- 2 weeks) (V8). At consent/screening visit (V1), baseline serum biochemistries, a general physical (including weight measurement) pregnancy test, impulsivity questionnaire (Binge Eating Scale [BES], depression screening (PHQ-9 [<https://patient.info/doctor/patient-health-questionnaire-phq-9>]), Minnesota Blast Exposure Screening Tool (MN-BEST), and executive function-related testing (NIH Examiner and Brain HQ) will be performed; these can be completed at V2 if those were not completed after consent on V1. These tests; other than the pregnancy, biochemistries, and PHQ-9; are repeated at V6-V8. While subjects are undergoing the 5 days of tDCS treatments (V2-V6) they will undergo Brain HQ testing during the treatment sessions. PHQ-9 is repeated at the final visit.

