### **Study Visit Details:**

#### ***Screening visit (Visit 1 [V1]):***

Subjects will be recruited from the clinic where Drs. [name] and [name] attend. Interested subjects will be screened for inclusion/exclusion criteria and review study details. Medical records will be reviewed for eligibility, and interested subjects will be consented if they are eligible. They will then undergo baseline blood draw (to include a comprehensive metabolic panel if not available within last 6 months, directed history and physical (including a weight measurement). If thyroid tests, (TSH alone or a TSH with a free T4), were not done and normal in the last 3 months for individuals taking thyroid hormone replacement, these will be done at baseline assessment. Baseline testing including the NIH Examiner Battery (which measures executive function domains), MN-BEST and BES (may either be done at the end of V1 or beginning of V2).

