#### ***tDCS session visits (V2-6):***

Subjects will go to the Minneapolis VAMC GRECC where they will undergo the tDCS sessions. Subjects will be randomly assigned to active vs. sham treatments which will occur on 5 sequential weekdays. The tDCS session will include a pre/post symptom rating questionnaire, 13 minutes of stimulation, a 20-minute stimulation break, followed by 13 more minutes of stimulation. Subjects will complete the Brain HQ test during stimulation and the stimulation break. The final stimulation visit, V6 will include NIH Examiner and their weight will be collected. These sessions will last around 1 hour to 1.5 hours each.

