#### ***Visits post tDCS intervention (V7 and V8):***

These visits will be identical to V1 with the exceptions that the history and physical, MN-BEST and blood draw will not be repeated; a weight measurement will be taken along with completion of the BES questionnaire, the Brain HQ and NIH Examiner. A short blinding questionnaire will be asked at V8 to assess the adequacy of tDCS blinding.

Table 1. Table of Assessments

Visit	Assessments	Stimulation	Duration	Compensation
Visit 1	HIPAA, Consent, NIH Examiner, BES, PHQ-9, Medication Review, MN-BEST, Blood Draw, Physical (Weight Measurement), Pregnancy Test (if applicable)	None	120 minutes	\$30
Visit 2-5	tDCS, Pre/Post SRQ, Brain HQ, Medication Review	tDCS	60 minutes	\$15
Visit 6	tDCS, Pre/Post SRQ, Brain HQ, NIH Examiner, Medication Review, Weight Measurement	tDCS	90 minutes	\$22.50
Visit 7-8 (follow-ups)	NIH Examiner, Medication Review, Brain HQ, BES, Weight Measurement, Visit 8 only: PHQ-9, Blinding Questionnaire	None	120 minutes	\$30
Total:			11.5 hours	\$ 172.50

tDCS Device: We will use the Neuroelectrics Starstim system, a wireless multichannel transcranial current stimulator. Periods of tDCS stimulation of 13 minutes will be twice a day, separated by 20 minutes, for five consecutive days (5 total tDCS stimulation sessions). Active tDCS: A 2-mA current will be administered via two circular carbon rubber core electrodes in saline-soaked surface sponges (25 cm^2), placed in a neoprene headcap with marked locations based on the 10-10 EEG system. The anodal stimulating electrode will be at location F4, over right dorsolateral prefrontal cortex (DLPFC) and cathodal electrode at location F3, over left DLPFC. This tDCS configuration has been shown to be effective for stimulating DLPFC. Sham tDCS: For sham stimulation, the electrodes will be placed at the same positions as for active stimulation (F3 and F4), but current will be ramped down immediately after the initial 30 s ramp up period. Thus, participants will feel the initial itching sensation associated with tDCS but will receive no active current for the rest of the stimulation period. This method of sham stimulation has been shown to be reliable (Gandiga, Hummel, & Cohen, 2006). The Starstim software supports the measurement of electrode impedance. Before each training session, the impedance of the electrodes will be checked and verified to be ≤10 KOhm. During a training

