## **14. Data Management**

Data Analysis Plan: For this pilot study participants will be randomized to either active or sham tDCS. For the trained task, growth curve analysis (GCA) examining individual variation of the growth rates over time will be done (across all 10 tDCS sessions and the subsequent follow-ups) to examine for change in individual trajectories over time. For the untrained task (NIH Examiner), GCA to evaluate for enhancement of executive function in the four domains from pre- to post-treatment as compared with the sham group will be analyzed. As a secondary aim we will evaluate weight loss response during and after the behavior modification program

and evaluate the effect of active vs. sham treatment on weight loss. Results from this study will inform larger follow up studies supported by external applications.

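### The Brain HQ growth curve has no stimulation-free starting score and pools on- and off-stimulation visits, so a single growth-rate comparison could miss or misread a tDCS effect

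*Combined protocol and SAP*

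**What the plan says.** **Is there a Brain HQ test before stimulation?** The sections disagree.

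- Section 6, Study Procedures, says that at V1 "executive function-related testing (NIH Examiner and Brain HQ) will be performed", and adds that "these can be completed at V2 if those were not completed after consent on V1". It does not say that a test moved to V2 must come before the current starts.
- The text on V7 and V8 describes those visits as matching V1 apart from named exceptions. Brain HQ is done at V7 and V8 and is not among the exceptions, which implies that it is also done at V1.
- The Visit 1 row of Table 1 reads "HIPAA, Consent, NIH Examiner, BES, PHQ-9, Medication Review, MN-BEST, Blood Draw, Physical (Weight Measurement", followed only by a pregnancy test. Brain HQ first appears in the row for Visits 2-5, which are tDCS visits.
- The screening-visit text lists "Baseline testing including the NIH Examiner Battery (which measures executive function domains), MN-BEST and BES", with no Brain HQ.

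**When are the later scores taken?** For V2-V6, "Subjects will complete the Brain HQ test during stimulation and the stimulation break". Study Design says that V7 and V8 have no stimulation.

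**What does the analysis use?** Study Design fits the curve "across the 5 days of tDCS sessions and the subsequent follow-ups", and section 14 fits it "across all 10 tDCS sessions and the subsequent follow-ups". Neither window reaches back to V1. Study Design refers both to individual growth rates and to an aim "to examine for change in individual and group trajectories over time". The documents give no time coding, functional form, baseline adjustment, phase term or group term for this model.

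**The concern.** Two features of the design combine here. First, the curve contains no score from before stimulation. A site that follows Table 1 would not collect one, and it could not be recovered later. Even if V1 is tested as Study Procedures says, both analysis windows leave the score out. Second, scores obtained while current may be running (V2-V6) and scores obtained without it (V7-V8) lie on the same trajectory, with nothing to separate the two conditions.

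A straight-line growth rate is a poor summary of that series. If active stimulation lifts performance at once and the lift lasts, the whole effect sits in the level of the curve and none in its slope. If the lift exists only under current, the active arm falls back relative to sham after V6, and a reader of the slope could conclude that tDCS harmed learning. At stake is the interpretation of the trained-task result, which is meant to show whether stimulation enhances training.

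**Working it through.** The plan gives no figure for the trained-task analysis. Its only power statement concerns the untrained tests and is not needed here.

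**Inputs from the documents:** five stimulation days (V2-V6), then V7 about 2 months into the class and V8 about 2 months later; 10 participants per arm; an effect of 0.97 SD (Statistical Plan), borrowed only as an illustrative size.

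**Assumptions:** test days 0, 1, 2, 3, 4, 60 and 120; one straight line; unweighted least squares.

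**Step 1. Slope of the arm difference.** The slope is Sxy/Sxx, with Sxy = sum(t·y) - tbar·sum(y) and y the active-minus-sham difference at each visit.

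- tbar = 190/7 = 27.143; Sxx = 18030 - 190²/7 = 12872.86.
- Immediate and lasting, y = (1,1,1,1,1,1,1): Sxy = 190 - 27.143×7 = 0. Slope 0.
- Only under stimulation, y = (1,1,1,1,1,0,0): Sxy = 10 - 27.143×5 = -125.71. Slope -0.00977 per day, or -1.17 by day 120.
- Gradual and lasting, y = (0.2,0.4,0.6,0.8,1,1,1): Sxy = 188 - 27.143×5 = 52.29. Slope +0.00406 per day, or +0.49 by day 120.

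The second result is not sensitive to the assumed dates. With V7/V8 at days 50/110, 63/126 or 74/134 it is again -1.17 by the last visit. With visits numbered 0-6, Sxx = 28, Sxy = 10 - 3×5 = -5, and the total over the span is (-5/28)×6 = -1.07.

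**Step 2. Simulated rejection rates.** Settings: 10 per arm, effect 0.97 SD, two-sided 0.05, assumed within-subject correlation 0.6, no random slopes, 20,000 runs (4,000 for ANCOVA). V1 is placed at day -7, or one visit before V2. Where two values appear, the first is visit coding and the second day coding.

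| Comparison | Immediate, lasting | Only under stimulation |
|---|---|---|
| Slope, V2-V8 | 0.05 | 0.86 / 0.95 (negative direction) |
| Mean level, V2-V8, no baseline | 0.72 | 0.44 |
| Single slope with V1 added | 0.42 / 0.13 | 0.24 / 0.82 (negative direction) |
| Mean change from V1 | 0.86 | 0.58 |
| ANCOVA on V1 | about 0.95 | 0.74 |

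**Step 3. What the baseline adds to a level comparison.** With unit variance and correlation r, the mean of seven visits has variance r + (1-r)/7. Adjusting for V1 subtracts r². The standard error of the arm difference is the root of that variance times sqrt(2/10). The small cost of estimating the covariate coefficient is ignored.

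| r | SE, no baseline | SE, adjusted for V1 | Reduction |
|---|---|---|---|
| 0.3 | 0.283 | 0.249 | 12% |
| 0.6 | 0.363 | 0.244 | 33% |
| 0.8 | 0.407 | 0.194 | 52% |

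**The case against.** The strongest reply is that the plan does not commit to a slope-only test. It refers to group trajectories, and a trajectory has a level as well as a rate. Because the arms are randomized, a difference in level over V2-V8 is a valid comparison without any baseline, and Step 2 gives it power of 0.72 at 0.97 SD. This stands. A reader might infer that an early arm difference could not be told apart from chance. The documents do not support that: what is lost without a baseline is precision.

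A reader might also blame Table 1 for the late start of the curve. The windows in Study Design and section 14 set the start, so correcting the table alone would change nothing in the analysis. Nor would adding V1 to a single line do much: power for the lasting effect reaches only 0.42 or 0.13. Most of the remedy lies in the model.

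The negative slope is not a false estimate. If the gain vanishes when the current stops, the arm difference really does fall; the risk is that the fall is read as harm. A gradual lasting gain, the pattern closest to the protocol's plasticity rationale, keeps the right sign.

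Finally, five days and ten sessions need not conflict: section 5 counts two stimulation periods a day for five days as ten sessions. But the device paragraph after Table 1 describes the same schedule as five sessions, and no section says how many Brain HQ scores a day yields. The time index still has to be stated.

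**Conclusion.** The point holds as a matter of specification. The sections disagree on whether a Brain HQ score is taken at V1, both analysis windows would leave it out, and one curve pools two testing conditions with no term to separate them. The consequence is conditional: if the arms are compared on a single linear growth rate, an immediate lasting effect contributes nothing, and an effect confined to stimulation shows as a relative decline of about 1.1 to 1.2 times its size over the follow-up span. Those figures rest on the straight-line form and the assumed time coding. The rejection rates rest also on the assumed correlation of 0.6 and an effect of 0.97 SD.

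It would go too far to conclude that the plan will miss an effect of tDCS on the trained task, since it does not exclude a comparison of levels. The trial's main conclusion is not at risk either: section 4, Study Endpoints, names the NIH Examiner score as primary and weight as secondary, and the NIH Examiner has its own baseline. This is a worthwhile, low-cost improvement to a supporting analysis.

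**What to change.** 1. Reconcile Study Procedures, the screening-visit text and Table 1 so that every participant has a Brain HQ score at V1, or at V2 before any current if the test is moved.
2. Use that score as the baseline covariate in the trained-task model, and say so in both Study Design and section 14.
3. Fit visit as categorical, or add a group-by-phase term (on or off stimulation), so that level and change are both compared between arms. Do not simply append V1 to one growth rate.
4. State one time index in both sections, including how many Brain HQ scores each stimulation day contributes.

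The cost is one short test run within a visit already scheduled for 120 minutes, slight practice exposure that is equal in both arms, some rewording, and a few more model parameters. With 20 participants those parameters are not free, and the phase term is more economical than fully categorical visits.
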